Premature patient withdrawal	Point/time when the patient exits from the study prior to the planned completion of all study drug administration and/or assessments; at this time all study drug administration is discontinued and no further assessments are planned
Randomization number	A unique identifier assigned to each randomized patient

Screen Failure	A patient who did not meet one or more criteria that were required for participation in the study
Source Data/Document	Source data refers to the initial record, document, or primary location from where data comes. The data source can be a database, a dataset, a spreadsheet or even hard-coded data, such as paper or eSource
Start of the clinical trial	The start of the clinical trial is defined as the signature of the informed consent by the first patient
Study treatment	Any single drug or combination of drugs or intervention administered to the patient as part of the required study procedures
Study treatment discontinuation	When the patient permanently stops taking any of the study drug(s) prior to the defined study treatment completion date (if any) for any reason; may or may not also be the point/time of study discontinuation
Subject	A trial participant (can be a healthy volunteer or a patient)
Treatment arm/group	A treatment arm/group defines the dose and regimen or the combination, and may consist of 1 or more cohorts.
Variable	A measured value or assessed response that is determined from specific assessments and used in data analysis to evaluate the drug being tested in the study
Withdrawal of study consent (WoC)	Withdrawal of consent from the study occurs only when a patient does not want to participate in the study any longer and does not allow any further collection of personal data

Protocol summary

Protocol number	CLCZ696DUS01
Full Title	A multicenter, randomized, double-blind, double-dummy, parallel group, active controlled study to evaluate the effect of sacubitril/valsartan (LCZ696) versus valsartan on changes in NT-proBNP, safety, and tolerability in HFpEF patients with a WHF event (HFpEF decompensation) who have been stabilized and initiated at the time of or within 30 days post-decompensation (PARAGLIDE-HF)
Brief title	Prospective comparison of ARNI with ARB Given following stabiLization In DEcompensated HFpEF (PARAGLIDE-HF)
Sponsor and Clinical Phase	Novartis, Phase IIIB
Investigation type	Drug
Study type	Interventional

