4.5 Risks and benefits

In order to minimize the interaction between an ACEi and sacubitril in potentiating the development of angioedema, patients cannot receive ACEi for 36 hours prior to the first dose of study medication. To help ensure this documented washout, patients currently or recently taking ACEi will not be eligible for randomization until at least 36 hours from their last ACEi dose. Medication administration records should be reviewed to insure no ACEi was administered for at least 36 hours prior to the first dose of study medication.

All patients will be allowed to continue receiving the rest of their background cardiovascular (CV) medications. The risk to patients in this trial will be minimized by compliance with the eligibility criteria and close clinical monitoring. A Data Monitoring Committee (DMC) will also monitor the study for all safety considerations, since this population represents a patient population who are being initiated on study drug during the same hospitalization for admission for acute decompensated heart failure.

Women of child bearing potential and sexually active males must be informed that taking the study treatment may involve unknown risks to the fetus if pregnancy were to occur during the study, and agree that in order to participate in the study they must adhere to the highly effective contraception requirements outlined in the exclusion criteria. If there is any question that the patient will not reliably comply, they should not be entered or continue in the study.

Participating patients will benefit from careful monitoring and follow-up during the entire study duration regardless of whether they are receiving study medication.

5 Population

The study population will consist of male and female patients, ≥ 18 years of age, currently hospitalized for or within 30 days of a WHF event (HFpEF decompensation). A WHF event (HFpEF decompensation) is defined as a hospitalization, emergency department (ED) visit or out-of-hospital urgent HF visit, all requiring IV diuretics. A total of approximately 450 patients

will be randomized to sacubitril/valsartan or valsartan in a 1:1 ratio at approximately 130 centers in the United States and Canada

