6.4 Dose modification

6.4.1 Dose modifications

For patients who do not tolerate the protocol-specified dosing schedule, dose interruptions and/or reductions are either recommended or mandated in order to allow patients to continue the study treatment.

Deviations to mandatory dose interruptions and/or reductions are not allowed. Permanent treatment discontinuation is mandatory for specific events listed in [Section 9.1.1](#).

These dose changes must be recorded on the appropriate case report form (CRF).

Every attempt should be made to maintain patients on the target study drug dose level for as long as possible throughout the study. If, however, in the opinion of the investigator, a patient is unable to tolerate the protocol-specified target dose, the investigator should consider whether dose adjustments of concomitant medications may rectify the situation before reducing the dose of study treatment. If adjustment of the concomitant medications is not possible or does not alleviate the side effects of concern, the investigator may down-titrate the dose of the study drug to the previous dose level. If needed, the study drug may be stopped completely, if this occurs, the patient should return to the clinic as soon as possible, after discontinuation of study drug, for an end of study visit. Patients may restart their current dose of study drug following an interruption of treatment, based on investigator judgment.

Study drug dose level adjustments should be mainly based on overall safety and tolerability with special focus on:

- Hyperkalemia
- Symptomatic hypotension
- Clinically significant decrease in eGFR/increase in serum creatinine (defined as a serum creatinine of $\geq 0.5\text{mg/dl}$ with at least a 25% decrease in eGFR)
- Angioedema

These changes must be recorded on the appropriate CRF. Every attempt should be made to titrate to and maintain patients on target study drug Dose Level 3 for as long as possible throughout the study. If, however, in the opinion of the investigator, a patient is unable to tolerate the protocol-specified target dose, the investigator will manage the patient's treatment according to the below guidelines:

Steps:

1. Adjust Concomitant Medications

- Dose adjustments/elimination of concomitant medications may remedy the situation before reducing the dose of study treatment. If adjustment of the concomitant medications is not possible or does not alleviate the side effects of concern, THEN;

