2. Adjust Study Treatment Dose Level

- Down-titrade study treatment to the previous dose level. The patient may continue receiving the lower dose level for a recommended period of 1 to a maximum of 4 weeks.
- A re-challenge to titrate back up to the target dose level should be attempted at 2 weeks, or when patient is deemed stable. THEN:

3. Further Adjust Study Treatment Dose Level

- If tolerability issues are not alleviated despite down-titration by one dose level, the investigator may down-titrade further to the next lower study treatment dose level. The patient may continue receiving the lower dose level for a recommended period of 1 to a maximum of 4 weeks. See Step 5.
- Again, once stable, the patient should be re-challenged with up-titration to the next higher dose level in an attempt to gradually bring the patient back to the target study treatment dose level (Dose Level 3).
- The investigator may choose the next dose level for down- or up-titration according to his or her clinical judgment.

4. Stopping Study Treatment

- If needed, the study treatment may be stopped completely, however, every effort must be made to complete an end of study visit and obtain follow up health status information and NT-proBNP for any patient that withdraws from the study.

5. Study drug restart after temporary treatment interruption

- Once the investigator considers the patient's condition appropriate for receiving the study drug, the investigator should re-start the patient on study treatment at the most appropriate and allowable dose level per his/her medical judgment.
- If tolerated, the patient should be titrated up to the next dose level every 1 to 4 weeks, as per the investigator's judgment.
- In some instances, Dose Level 1 or 2 could be maintained if the investigator considers that the patient's condition would not allow any further up-titration to the target dose of study medication (Dose Level 3). In this case, it would be acceptable to maintain the patient at Dose Level 1 or 2, whichever is the higher and tolerated dose level by the patient, but reasons for not getting to Dose Level 3 need to be captured in the eCRF.
- Should the patient not tolerate the re-start study drug dose level, he/she may be down-titrated again (if appropriate) or discontinued from study treatment.

Patients re-started on the study drug will retain their original randomization and study identification numbers.

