The IRT must be contacted to register any changes in the patient's study treatment dose level, including in cases of temporary and permanent withdrawal or re-start of the study drug, and to obtain the medication numbers of the study drug supplies required for the new study treatment dose level. All dose changes and interruptions must also be recorded on the appropriate eCRF.

Study visits should occur as close as possible to the pre-defined visit and time schedule described in [Table 8-1](#). The timeframe between the regular visits should be maintained as scheduled, irrespective of the number of unscheduled visits that may be performed in between, or dose interruptions that may occur.

In case of pregnancy discovered during the study, the patient should be instructed to stop taking the study drug immediately.

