9.1 Discontinuation

9.1.1 Discontinuation of study treatment

Discontinuation of study treatment for a patient occurs when study treatment is stopped earlier than the protocol planned duration, and can be initiated by either the patient or the investigator.

The investigator must discontinue study treatment for a given patient if he/she believes that continuation would negatively impact the patient's well-being.

Study treatment must be discontinued under the following circumstances:

- Patient/guardian decision
- Pregnancy
- Use of prohibited treatment as per recommendations in the prohibited treatment section
- Any situation in which study participation might result in a safety risk to the patient
- Following emergency unblinding
- Any severe suspected drug related AE at the investigator's discretion

- Suspected occurrence of angioedema. A patient with any signs or symptoms of clinically significant angioedema should be thoroughly evaluated by the investigator to determine if it constitutes a reason for discontinuation of study medication.
- Depending on the serum potassium, blood pressure, or eGFR, patient may need to have their study drug dose or the dose of another concomitant medication reduced or discontinued; or, if appropriate, have potentially contributing agents adjusted. Refer to appendices for treatment guidelines for hyperkalemia, hypotension or renal dysfunction, respectively.

If discontinuation of study treatment occurs, the investigator should make a reasonable effort to understand the primary reason for the patient's premature discontinuation of study treatment and record this information.

Patients who discontinue study treatment or who decide they do not wish to participate in the study further should NOT be considered withdrawn from the study UNLESS they withdraw their consent (see withdraw of informed consent section.). **Where possible, they should return for the assessments indicated** in the assessment schedule. If they fail to return for these assessments for unknown reasons, every effort (e.g. telephone, e-mail, letter) should be made to contact the patient/pre-designated contact as specified in the lost to follow-up section. This contact should preferably be done according to the study visit schedule.

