For participants recruited under the Protocol Version 00 (Original Protocol) who do not continue in amendment protocol assessments performed at Weeks 10 or 12 (including, but not limited to, vital signs) are assigned to the open label phase for summarization purposes, unless otherwise noted. Unscheduled assessments are not assigned to a study phase for purposes of by-visit summaries.

For summarization of AEs, notable vital signs and laboratory abnormalities, and symptomatic hypotension by study phase, an assessment during the open label phase is defined as any assessment obtained in the following time interval:

After the date of the Week 8 visit. For participants without a Week 8 visit, a projected Week 8 visit date will be derived relative to their treatment start date.

Participants enrolled under Protocol Version 00 (Original Protocol) who died, withdrew consent, or were lost to follow-up prior to or on their projected Week 8 visit date will be excluded from the open-label phase.

End of Study (EOS)

EOS is obtained directly from the source data. A subject can discontinue treatment (EOT) at any time but continue the study, then the EOS is the study completion date. A subject who completes the study and has an EOS visit. If a subject discontinues the study for any reason, the discontinuation date is the EOS for that subject.

Follow-up for time-to-event analyses

For patients enrolled in the original protocol and continue to an open-label period, events are considered up to the end of their double-blind period (up to Week 8). For patients enrolled in Protocol Amendments 1-4, the events are considered up to their end of double-blind phase (EOS).

In-Hospital / Out-of-Hospital Randomization Status

The status for patient's in-hospital/out-of-hospital randomization is collected as "In-Patient or Out-Patient" category and will be provided by the Interactive Response Technology (IRT).

Year, month and week

For reporting purposes, the rules below will be followed to convert a year, month and week to days.

1 year = 365.25 days

1 month = 30.4375 days

1 week = 7 days

1 day = 24 hours

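### Protocol 6.4.1 links stopping study drug to an end of study visit, 9.1.1 keeps such patients in the study, and neither secures the off-drug Week 4 and Week 8 NT-proBNP that the treatment-policy primary estimand needs

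*Protocol*

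**What the plan says.** **What happens when drug is stopped.** Protocol 6.4.1 provides for stopping study drug completely and then says "the patient should return to the clinic as soon as possible, after discontinuation of study drug, for an end of study visit". The trigger is stopping drug, not leaving the study. Step 4 of the same section, headed as being about stopping study treatment, asks sites to complete an end of study visit and "obtain follow up health status information and NT-proBNP for any patient that withdraws from the study". The heading concerns treatment; the sentence concerns study withdrawal.

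**Staying in the study.** Protocol 9.1.1 says patients who discontinue treatment "should NOT be considered withdrawn from the study UNLESS they withdraw their consent" and should come back for scheduled assessments where possible. For patients who cannot attend, it allows abbreviated contacts, including telephone or email. The stated minimum content is treatments and adverse events; NT-proBNP is not listed. Other text points the same way as 9.1.1:
- The glossary says that stopping treatment "may or may not also be the point/time of study discontinuation".
- Protocol 4.5 promises "follow-up during the entire study duration regardless of whether they are receiving study medication".
- Later in 6.4.1: "The timeframe between the regular visits should be maintained as scheduled", whatever dose interruptions occur.
- SAP 2.1.1, on end of study: "A subject can discontinue treatment (EOT) at any time but continue the study, then the EOS is the study completion date".

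**What the primary analysis needs.** SAP 2.5.2 (Estimand 1) applies treatment policy to treatment discontinuation. SAP 2.5.3 does not impute missing values and does not use NT-proBNP from unscheduled visits. Protocol 12.4.2 leaves out a patient with no baseline, or with neither Week 4 nor Week 8. Central NT-proBNP is scheduled only at Visits 2, 3, 5 and 7 (Protocol 8.3.3), so the end of study visit (Visit 17) is not an NT-proBNP time point.

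**The concern.** A treatment-policy estimand is only as good as the follow-up of patients who stop treatment. Here the section a site consults when stopping drug points to a visit that shares its name with Visit 17. Protocol 8 gives a similar as-soon-as-possible instruction for patients who discontinue the study. In the glossary, premature withdrawal means that "at this time all study drug administration is discontinued and no further assessments are planned". A site that takes 6.4.1 as study exit would therefore not collect later Week 4 or Week 8 samples.

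Two things could be lost. The first is off-drug NT-proBNP, which would tilt the primary analysis toward patients still on drug. The exposure is greatest for stops before Week 4, because one post-baseline value is enough to stay in the analysis. The second is clinical-event follow-up: SAP 2.1.1 runs time-to-event follow-up to end of study, and the win-ratio time at risk in SAP 2.6.2.1.1 lists the End of Study visit date. An end of study recorded at drug stop would shorten both.

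**Working it through.** **1. The texts side by side**

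| Source | Trigger | Consequence |
|---|---|---|
| Protocol 6.4.1, main text | Drug stopped completely | End of study visit as soon as possible |
| Protocol 6.4.1, step 4 | Heading: stopping treatment; sentence: withdrawing from the study | End of study visit, health status, NT-proBNP |
| Protocol 9.1.1 | Drug stopped, consent not withdrawn | Not withdrawn; scheduled assessments where possible |
| Protocol 9.1.1, abbreviated visits | Drug stopped | Minimum data: treatments and adverse events, no NT-proBNP |
| SAP 2.1.1 | Drug stopped, study continued | End of study is the study completion date |

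The main text of 6.4.1 is the outlier. No row expressly secures NT-proBNP at Weeks 4 and 8 after drug is stopped in a patient who stays in the study.

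**2. The plan's own figure**

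Inputs (Protocol 12.8, SAP 3): N = 450, 1:1; ratio 0.77; SD 0.85; two-sided 0.05; 15% missing.
- Evaluable per arm: 450 × 0.85 / 2 = 191.25.
- SE = 0.85 × √(2/191.25) = 0.0869.
- ln(0.77) = −0.2614, and 0.2614 / 0.0869 = 3.01.
- Power is 85.2% by the normal approximation, or 85.0% by the noncentral t with 191 per arm. The stated 85% reproduces.

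**3. Illustration of the possible bias**

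The documents give no discontinuation rate and no off-drug effect, so everything here is assumed. Let L = ln(0.77) be the effect in patients who continue drug. Let d be the fraction of each arm that stops before both visits, u the fraction of these left unmeasured, and f the fraction of the effect lost. The range of d is capped at the planned 15% missingness, which covers all causes.
- Treatment-policy ratio = exp(L × (1 − d·f)).
- Observed ratio = exp(L × [(1 − d) + d(1 − u)(1 − f)] / (1 − d·u)).
- n per arm = 225 × (1 − d·u); SE = 0.85 × √(2/n).
- Gap = difference of the two log ratios.

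| f | u | d | Treatment-policy ratio | Observed ratio | Log gap | SE | Gap/SE |
|---|---|---|---|---|---|---|---|
| 1 | 1 | 5% | 0.780 | 0.770 | 0.0131 | 0.0822 | 0.16 |
| 1 | 1 | 10% | 0.790 | 0.770 | 0.0261 | 0.0845 | 0.31 |
| 1 | 1 | 15% | 0.801 | 0.770 | 0.0392 | 0.0869 | 0.45 |
| 1 | 0.5 | 5% | 0.780 | 0.775 | 0.0064 | 0.0812 | 0.08 |
| 1 | 0.5 | 10% | 0.790 | 0.781 | 0.0124 | 0.0822 | 0.15 |
| 1 | 0.5 | 15% | 0.801 | 0.787 | 0.0180 | 0.0833 | 0.22 |

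Worked row (f = 1, u = 1, d = 10%): the treatment-policy log ratio is −0.2614 × 0.90 = −0.2352, so the ratio is 0.790. The gap is 0.2614 − 0.2352 = 0.0261 before rounding, n = 225 × 0.90 = 202.5, and 0.0261 / 0.0845 = 0.31.

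If half the effect is lost and none is measured, the gap is 0.08, 0.16 and 0.23 SE at 5%, 10% and 15%. If no effect is lost (f = 0), the gap is zero.

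**The case against.** The strongest reply is that the harm depends on a reading that the protocol resists. Section 6.4.1 does not cancel later visits. Its next sentence allows restart, it keeps visit timing despite interruptions, and it sends the reader to 9.1.1 for mandatory permanent discontinuation, where the rule is emphatic. The final-visit rule in Protocol 8 and the glossary entry on premature withdrawal both concern patients who leave the study, not patients who stop drug. This stands in part. A reader might infer that 6.4.1 takes these patients out of the study; the text leaves that reading open but does not state it.

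Three other inferences go too far:
- *That the SAP requires follow-up unless consent is withdrawn.* SAP 2.1.1 only says a subject can continue, does not mention consent, and serves to define a date.
- *That following 9.1.1 would be enough.* Its wording is conditional and its minimum data omit NT-proBNP, so samples can be lost under 9.1.1 as well.
- *That the visit windows are left open.* SAP 2.4.3 assigns them by recruitment version: Week 4 and Week 8 are Days 22–35 and 50–63 for versions 00 to 03, and Days 18–42 and 43–112 for Amendment 04.

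The plan also has some mitigation. Sensitivity analysis 1 (SAP 2.5.4) multiply imputes missing Week 4 and Week 8 values under missing at random. But its imputation model is specified on the three NT-proBNP measurements and does not use discontinuation status, so it does not replace observed off-drug values.

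Finally, the largest figure, 0.45 SE, needs the whole missingness allowance to be early stoppers, none measured, with the effect entirely gone. That is correct, and it should be read as an illustration only.

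**Conclusion.** The conflict is in current text and bears on the primary estimand: one section attaches an end of study visit to stopping drug, while another keeps the patient in the study. Separately, the post-discontinuation minimum does not include the primary endpoint sample. That is worth correcting.

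The size and direction of any bias are unknown. Under the assumptions shown, it ranges from zero to 0.45 SE, and from 0.08 to 0.22 SE if half of those who stop are measured and the effect is fully lost. How much of this would trace to 6.4.1 depends on how sites read it, and many may follow 9.1.1. A reader might infer that the sample size or power is wrong. It is not: the 85% reproduces with the 15% allowance. Confidence is medium, and the point is a should-fix.

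**What to change.** These changes concern data collection only. They do not alter when or why study drug is stopped.

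1. Reconcile the main text and step 4 of Protocol 6.4.1 with 9.1.1. Stopping drug without withdrawing consent should not replace the scheduled visits with an end of study visit. State that the Week 4 and Week 8 central NT-proBNP draws and clinical-event follow-up continue.
2. Add NT-proBNP at Weeks 4 and 8 to the post-discontinuation data listed in Protocol 9.1.1.
3. As a minor addition, say in SAP 2.5.3 whether an NT-proBNP from an early end of study visit that falls in a Week 4 or Week 8 window counts as unscheduled. The windows need no change.

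Cost: a protocol amendment with IRB/IEC approval (Protocol 14.1), a memo to sites and one SAP sentence. No draws are added, because Weeks 4 and 8 are already scheduled.
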